10.3. General Statistical Considerations

The statistical analyses will be performed using R, version 4.1.2 or higher. Any statistical tests of hypotheses will employ a level of significance of alpha=0.05.

11. SAMPLE SIZE JUSTIFICATION

There is no particularly relevant sample size justification with a single-arm study. It is worth noting that prior studies with between 30 and 35 subjects in any given study group have allowed successful distinctions to be made in the performance of different trifocal IOLs, including PanOptix.³ It is expected that 32 subjects (64 eyes) will provide sufficient data to characterize the clinical performance of the lens. To allow for 10% dropout, 35 subjects (70 eyes) will be enrolled.

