9.2.2. Operative (Surgery)

All subjects will undergo cataract surgery with implantation of the Clareon PanOptix IOL. The surgeon's usual standard of care with regard to treatment and medication will be used for all study subjects. Surgery planning and IOL power calculation will be performed using the surgeon's preferred method, with an initial a-constant provided by Alcon. If a toric IOL is used, planning will be performed with the Alcon Toric calculator that takes the effects of posterior corneal astigmatism into account.

Surgical findings will be recorded and any adverse events/serious adverse events (AEs/ SAEs) occurring during surgery will be noted at this visit. Any other problems during surgery and comments regarding surgery will be documented.

Any subject whose surgery is not completed successfully will be documented in the appropriate case report form. These subjects will be monitored for safety but clinical performance data may be excluded from the analysis.

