10. ANALYSIS PLAN

10.1. Analysis Data Sets

All subjects who are enrolled in the study will be evaluated for safety. Efficacy analyses will be performed based on data from those eyes where uncomplicated cataract surgery with PanOptix IOL implantation was completed.

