18.2. Patient Discontinuation

Each study patient may voluntarily discontinue the study at any time they choose. Study patients who cannot complete the study for administrative reasons (e.g., non-compliance, failure to meet visit schedule, etc.) will be discontinued from the study. Study patients discontinued during the enrollment phase (prior to surgery) of the study will be replaced.

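### Does enrolling 35 subjects fail to leave the planned 32 after 10% dropout?

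*Combined protocol and SAP*

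**What the plan says.** Section 11 opens by setting a formal calculation aside: "There is no particularly relevant sample size justification with a single-arm study". It offers experience as its basis instead, noting that "prior studies with between 30 and 35 subjects in any given study group have allowed successful distinctions to be made". The target comes next: "It is expected that 32 subjects (64 eyes) will provide sufficient data to characterize the clinical performance of the lens". The allowance for losses follows: "To allow for 10% dropout, 35 subjects (70 eyes) will be enrolled".

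Other sections affect how many subjects reach the efficacy analysis:

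- Section 10.1 (Analysis Data Sets): "Efficacy analyses will be performed based on data from those eyes where uncomplicated cataract surgery with PanOptix IOL implantation was completed".
- Section 9.2.2 (Operative), on subjects whose surgery is not completed successfully: "These subjects will be monitored for safety but clinical performance data may be excluded from the analysis".
- Section 7.3 (Exclusion Criteria) lets the principal investigator class a patient as non-evaluable on medical evidence, and allows data from subjects who become pregnant to be left out of effectiveness analyses.
- Section 18.2 (Patient Discontinuation): "Study patients discontinued during the enrollment phase (prior to surgery) of the study will be replaced".
- Section 18.3 (Patient Termination) does not replace patients terminated for a severe adverse event that may be related to the study.

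The primary outcome (Sections 3 and 8.1) is binocular, so each subject gives one value per visit.

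**The concern.** Three things look wrong on a first reading.

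First, an allowance for 10% loss should leave the target after 10% are lost, and 35 less 10% is not 32.

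Second, dropout is the only loss Section 11 names, yet other sections remove subjects or eyes from efficacy for other reasons. Only losses before surgery are replaced. Because the primary outcome needs both eyes, one complicated eye could cost a subject's primary value. If these exclusions come on top of dropout, the final number falls further below 32.

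Third, the target is given in eyes as well as subjects. A reader who took 64 as the number of independent observations on a binocular outcome would think the study more precise than it is.

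At stake would be a final sample smaller than the plan claims, and an overstated impression of its information content.

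**Working it through.** **Inputs.** From Section 11: target 32 subjects, dropout 10%, enrolment 35, benchmark 30 to 35 subjects per group. The documents give no standard deviation, margin, power or rate of post-surgery exclusion. Precision is therefore expressed in units of the standard deviation (SD), and exclusion rates are assumed over a range.

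**Reproducing 35.**

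- Strict inflation, N/(1 − d): 32/0.90 = 35.56, rounded up to 36.
- Simple inflation, N × (1 + d): 32 × 1.10 = 35.2, which is 35 to the nearest whole number and 36 rounded up.
- Reverse check: 35 × 0.90 = 31.5, against 36 × 0.90 = 32.4.
- Losses tolerated: 35 − 32 = 3, and 3/35 = 8.6%. A fourth loss (4/35 = 11.4%) leaves 31.

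The stated 35 is thus simple inflation rounded to nearest, one subject below the strict answer.

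**Chance of keeping 32.** If each subject drops out independently with probability 0.10, the binomial probability that at least 32 remain is 0.53 with 35 enrolled and 0.71 with 36. Even the strictly inflated number misses 32 in 29% of cases, because inflation by expected loss gives no guarantee. The 0.53 is mostly a consequence of that method; the rounding accounts for the difference of 0.18.

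**Effect on precision.** The half-width of a 95% confidence interval for a mean, in SD units, is t(0.975, n − 1)/√n:

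| n | Half-width (SD) |
|---|---|
| 35 | 0.344 |
| 32 | 0.361 |
| 31 | 0.367 |
| 30 | 0.373 |
| 28 | 0.388 |

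Going from 32 to 31 widens the interval by a factor of 0.367/0.361 = 1.017, under 2%.

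**Post-surgery exclusions.** Suppose a further fraction e of subjects is excluded in addition to the 10% (an assumption). The expected number from 35 is 35 × 0.90 × (1 − e), and the enrolment needed for 32 is 32/(0.90 × (1 − e)), rounded up:

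| e | Expected from 35 | Enrolment for 32 |
|---|---|---|
| 0% | 31.5 | 36 |
| 2% | 30.9 | 37 |
| 3% | 30.6 | 37 |
| 5% | 29.9 | 38 |
| 10% | 28.4 | 40 |

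Up to about 5% additional exclusion, the expected number stays at about 30, the lower end of the plan's own benchmark. At 10% it falls below that range, and the half-width at n = 28 is 0.388 SD, against 0.361 SD at 32.

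**Eyes and subjects.** Treating 64 eyes as independent would give t(0.975, 63)/√64 = 1.998/8 = 0.250 SD. The plan makes no such calculation. Section 11 puts subjects first and eyes in parentheses, and Section 7.1 requires both eyes of each subject to be enrolled. Eye counts have their own use: Table 15.1 schedules monocular distance acuity, and Section 10.1 defines efficacy eligibility by eye.

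**The case for a change.** The strongest case for a change is that 32 after 10% loss is the one target that Section 11 sets, and two sentences would put it right at no cost in subjects. Section 11 says dropout, not exclusion, and the restriction in Section 10.1 is mandatory. If exclusions of 2%, 3% or 5% are added to dropout, the chance of keeping at least 32 falls to 40%, 33% or 23%.

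Part of this stands. The strict number is 36, and Section 11 leaves open whether the 10% includes exclusions after surgery. A sentence saying that 35 enrolled allows three losses or exclusions to leave 32 would be a harmless clarification.

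It does not establish a shortfall, however. Dropout is not defined in Section 11. The list of reasons for discontinuation in Section 9.5 is broad, including protocol violation, treatment failure and an open category, so the 10% can be read as covering losses of every kind. The exclusions in Sections 7.3 and 9.2.2 are discretionary, and no section gives a rate. The lower probabilities therefore depend both on an assumed rate and on reading the exclusions as additional, which is the point in dispute.

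**Conclusion.** The concern is right on the arithmetic but calls for no change. The discrepancy is a rounding difference: 31.5 against 32 in expectation, or 35 against 36 in enrolment. No power, margin or precision target depends on 32, and 31 subjects lie within the 30 to 35 that the plan cites. Rewording Section 11 while keeping 35 enrolled would alter no analysis, result or conclusion.

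The silence on post-surgery exclusions is a gap that analysts fill in the ordinary way, by reporting how many subjects were enrolled, operated on, excluded and analysed; Section 10.2 already includes the sample size in its summaries of continuous variables. The eye count is not used as the sample size for the binocular primary outcome, so nothing needs to be withdrawn there.

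This rests on two assumptions: that total losses stay near the planned 10%, with no more than about 5% further exclusion, and that the study remains descriptive with no threshold to meet. Heavier exclusion would bring the number below the cited range, but nothing in the documents indicates that it should be expected.

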12. CONFIDENTIALITY/PUBLICATION OF THE STUDY

The existence of this Study is confidential and should not be discussed with persons outside of the Study. Results will be submitted for publication and presentation at national and/or international meetings. A manuscript will be submitted to peer-review journals for publication but there is no guarantee of acceptance.

All study data will be collected on appropriate Case Report Forms (CRFs). No protected health information will be included on the forms. CRFs will be retained in the patient's file for a minimum period of 3 years. Collected information will only be used for purposes of this study and no information will be sold to third parties. The following people will have access to your study records:

- Study Doctor and staff involved with the study
- Study Monitor or Auditor
- Sponsor Company or Research Institution
- Review boards or accrediting agencies
- Other State or Federal Regulatory Agencies

The de-identified data may be shared with other researchers for future analysis.

13. QUALITY COMPLAINTS AND ADVERSE EVENTS

All subjects will be monitored for adverse events over the course of the study. A place to record any adverse event is included on each case report form.

13.1. General Information

An Adverse Event (AE) is any untoward medical occurrence in a subject who is administered a study treatment regardless of whether or not the event has a causal relationship with the treatment. An AE, therefore, can be any unfavorable or unintended sign (including an abnormal laboratory finding), symptom, or disease temporally associated with the study treatment, whether or not related to the treatment. In clinical studies, an AE can include an untoward medical occurrence occurring at any time, including run-in or washout periods, even if no study treatment has been administered.

13.2. Monitoring for Adverse Events

At each visit, after the subject has had the opportunity to spontaneously mention any problems, the Investigator should inquire about AEs by asking if the patient has any problems.

13.3. Procedures for Recording and Reporting AEs and SAEs

Subsequent to signing an informed consent form, all untoward medical occurrences that occur during the course of the study must be documented on an Adverse Event Form

(AEF). A separate AEF must be filled out for each event. When possible, signs and symptoms indicating a common underlying pathology should be documented as one comprehensive event. For each recorded event, the AE documentation must include the onset date, outcome, resolution date (if event is resolved), intensity (i.e., severity), any action with study treatment taken as a result of the event, and an assessment of the adverse event's relationship to the study treatment.

Nonserious Adverse Events

A nonserious AE is defined as any untoward change in a subject's medical health that does not meet serious criteria noted below (e.g., is not life-threatening, does not require hospitalization, does not prolong a current hospitalization, is not disabling, etc.). All adverse events must be reported regardless of whether or not they are related to the study treatment.

For nonserious adverse events, an AEF containing all available information will be collected on a routine basis and submitted to the Medical Monitor at the close of the study.

Serious Adverse Events

A serious adverse event (SAE) is defined as any adverse experience that meets any of the following criteria:

- Results in death.
- Is life-threatening.

NOTE: Life-threatening means that the subject was at immediate risk of death from the reaction as it occurred; i.e., it does not include a reaction which hypothetically might have caused death had it occurred in a more severe form.

- Requires inpatient hospitalization or prolongation of existing hospitalization.
NOTE: In general, hospitalization signifies that the individual remained at the hospital or emergency ward for observation and/or treatment (usually involving an overnight stay) that would not have been appropriate in the physician's office or an out-patient setting. Complications that occur during hospitalization are AEs. If a complication prolongs hospitalization or fulfills any other serious criteria, the event is serious. When in doubt as to whether "hospitalization" occurred, the event should be considered serious.
- Results in persistent or significant disability/incapacity. Disability is defined as a substantial disruption of a person's ability to conduct normal life functions.
NOTE: The term disability means a substantial disruption of a person's ability to conduct normal life functions. This definition is not intended to include experiences of relatively minor medical significance such as uncomplicated headache, nausea, vomiting, diarrhea, influenza, or accidental trauma (e.g., sprained ankle) which may interfere or prevent everyday life functions but do not constitute a substantial disruption.
- Is an important medical event. An important medical event is an event that may not result in death, be life-threatening, or require hospitalization but may be considered an SAE when, based upon appropriate medical judgment, it may jeopardize the subject and may require medical or surgical intervention to prevent one of the

outcomes listed in the definitions for SAEs. Examples of such medical events include allergic bronchospasm requiring intensive treatment in an emergency room or at home, blood dyscrasias or convulsions that do not result in subject hospitalization, or the development of drug dependency or drug abuse.

All available information on a serious adverse event(s) and any other associated AE, if applicable, must be forwarded to the study coordinator for forwarding to the Medical Monitor immediately (i.e., within one working day of the Investigator's or site's knowledge of the event) as follows:

- In studies utilizing EDC (electronic data capture), all available information for the SAE and any associated AE(s) must be entered immediately into the EDC system.
- Additional information for any applicable event is to be reported as soon as it becomes available.

In addition to the reporting of serious adverse events to the study Medical Monitor, the SAE must be reported to the IRB / IEC according to their requirements.

The investigator must document all adverse device events (serious and nonserious but related) and all serious adverse events (related and unrelated) on the Adverse Device Effect and Serious Adverse Event Form. Any device quality complaints will also be documented.

- **Both the Quality Complaint Form and the Adverse Device Effect and Serious Adverse Event Form must be e-mailed immediately to the study coordinator.**
- **Additional relevant information is to be reported as soon as it becomes available.**

Study coordinator contact information is provided below.

**Table 13.3.-1:
Contact Information for the Study**

Study Staff (Coordinator)	Business Phone	e-mail	24-hour Office Phone

12.3.1 Intensity and Causality Assessments

For every adverse event and quality complaint, the investigator must assess the causality as Related or Not Related to the medical device under investigation. An assessment of causality will also be performed by the Medical Monitor utilizing the same definitions, as shown below:

Causality

Related	An adverse event or quality complaint classified as related may be either definitely related or possibly related where a direct cause and effect relationship with the medical device has not been demonstrated, but there is a reasonable possibility that the adverse event or quality complaint was caused by the medical device.
Not Related	An adverse event or quality complaint classified as not related may either be definitely unrelated or simply unlikely to be related (i.e., there are other more likely causes for the adverse event or quality complaint).

Where appropriate, the investigator must assess the intensity (severity) of the adverse event as mild, moderate, or severe based on medical judgment with consideration of any subjective symptom(s), as defined below:

Intensity (Severity)

Mild	An adverse event is mild if the subject is aware of but can easily tolerate the sign or symptom.
Moderate	An adverse event is moderate if the sign or symptom results in discomfort significant enough to cause interference with the subject's usual activities.
Severe	An adverse event is severe if the sign or symptom is incapacitating and results in the subject's inability to work or engage in their usual activities.

The investigator must document any action taken (i.e., medication, intervention, or treatment plan) and outcome of the adverse event or quality complaint when applicable.

13.4. Follow-Up of Adverse Events and Quality Complaints

The investigator is responsible for adequate and safe medical care of subjects during the study and for ensuring that appropriate medical care and relevant follow-up procedures are maintained after the study. Any additional data from these follow-up procedures must be documented and available to the study coordinator who, with the Medical Monitor, will determine when the data need to be documented on the CRFs.

13.5. Safety Analyses

The type, severity, duration and frequency of reported ocular adverse events will be tabulated. Adverse events will also be summarized for events that were considered treatment-related.

14. GCP, ICH and ETHICAL CONSIDERATIONS

This study will be conducted in compliance with Good Clinical Practices (GCPs), including International Harmonization (ICH) Guidelines, and in general, consistent with the 1996 version of the Declaration of Helsinki. In addition, all applicable local, state and federal requirements will be adhered to.

This study is to be conducted in accordance with Institutional Review Board regulations. The investigator will obtain appropriate IRB/ethics committee approval prior to initiating the study.

The study will be registered with clinicaltrials.gov.

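### Section 13.5 summarises only ocular and treatment-related adverse events, so a non-ocular event judged unrelated, even a serious one, would appear in no planned table

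*Combined protocol and SAP*

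**What the plan says.** Collection is comprehensive. Under section 13.3, once consent is signed, "all untoward medical occurrences that occur during the course of the study must be documented on an Adverse Event Form". The same section adds: "All adverse events must be reported regardless of whether or not they are related to the study treatment". It goes on to define serious events and gives them expedited handling through the study coordinator to the Medical Monitor, with reporting to the IRB/IEC as well.

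The analysis commitment in section 13.5 is two sentences. The first is "The type, severity, duration and frequency of reported ocular adverse events will be tabulated". The second is "Adverse events will also be summarized for events that were considered treatment-related". Nothing else is promised.

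Causality is covered in the subsection headed 12.3.1, which sits within section 13.3. There, "the investigator must assess the causality as Related or Not Related to the medical device under investigation", and "An assessment of causality will also be performed by the Medical Monitor utilizing the same definitions". Section 13.5 does not say which of the two assessments defines its treatment-related summary.

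On the population, section 10.1 states: "All subjects who are enrolled in the study will be evaluated for safety". Section 18.2 states: "Study patients discontinued during the enrollment phase (prior to surgery) of the study will be replaced". No section gives the divisor for adverse event percentages, or says whether ocular events are counted by eye or by subject.

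**The concern.** The planned tables are narrower than the data collected. If 13.5 is followed as written, a death or hospitalisation that is neither ocular nor judged related is recorded, forwarded and then left out of the study's safety results. A reader of the final tables could not tell that no such event occurred from the fact that none was tabulated.

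For non-ocular events, the relatedness judgement alone decides whether an event is shown. The study is unmasked and has no control arm, so that judgement cannot be checked against a comparison group. Under 12.3.1 the unrelated class also takes in events that are merely unlikely to be related. With two assessors and no rule for disagreement, the same event could be in or out of the summary depending on whose form is used. There is a further looseness: 12.3.1 asks about a relation to the device, while 13.5 speaks of treatment.

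**Working it through.** **Step 1: set collection beside analysis.** Cross the two attributes on which 13.5 selects.

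| Event class | Recorded under 13.3 | Ocular tabulation in 13.5 | Treatment-related summary in 13.5 |
|---|---|---|---|
| Ocular, related | yes | yes | yes |
| Ocular, not related | yes | yes | no |
| Non-ocular, related | yes | no | yes |
| Non-ocular, not related | yes | no | no |

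The fourth row is in no planned output. Seriousness appears in neither sentence of 13.5, so a serious event in that row is treated like any other.

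**Step 2: look for a summary elsewhere.** Section 10.2 promises data summaries, but for measurement time points and for eyes completing the study. It describes measured variables and does not supply an event table. The expedited route in 13.3 produces individual reports, not a summary.

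**Step 3: number of subjects.** Section 11 wants 32 subjects and enrols 35 to allow 10% dropout. Check: 32/0.9 = 35.6, and 35 × 0.9 = 31.5. The stated 35 is within one subject of the computed 36 and is used below.

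**Step 4: size of one omission.** 1/35 = 2.9% of subjects. For context, an observed 0/35 has an exact two-sided 95% upper limit of 1 − 0.025^(1/35) = 10.0%. That limit reflects the precision of a small study; it does not measure under-reporting.

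**Step 5: how likely an omission is.** Let p be the per-subject chance, over follow-up, of a non-ocular adverse event judged unrelated. The documents give no value, so p is assumed over a range. It covers all such events, not only serious ones. The chance of at least one among 35 is 1 − (1 − p)^35:

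- p = 1%: 29.7%
- p = 2%: 50.7%
- p = 5%: 83.4%
- p = 10%: 97.5%

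**Step 6: unit and divisor.** One affected eye is 1/70 = 1.43% of eyes but 1/35 = 2.86% of subjects, a factor of two that turns only on the unstated unit.

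For the divisor, suppose k subjects leave before surgery and are replaced, so that 35 are operated and 35 + k are enrolled. The value of k is not in the documents; take 0 to 5. One event is then 1/35 = 2.86% at k = 0, 1/36 = 2.78% at k = 1 and 1/40 = 2.50% at k = 5. The relative reduction k/(35 + k) is 0%, 2.8% and 12.5%.

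**The case against.** The strongest reply is that the omission is narrow. All reported ocular events are tabulated with no relatedness filter, and for an intraocular lens those matter most. Non-ocular events considered related are also summarised, and 12.3.1 defines related broadly enough to include possible relations. Serious events are not lost: each goes to the Medical Monitor within one working day and to the IRB/IEC, and a dedicated form covers serious events whether related or not. All of this stands, and it limits the consequence. It does not close the gap, because case-by-case oversight puts nothing in the study's results.

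Three stronger readings are tempting, and the documents do not support them.

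- A reader might infer that event rates will be diluted by subjects who were never operated, since the safety set is everyone enrolled and pre-surgery discontinuations are replaced. But no divisor is stated, the number of such subjects is unknown, and the effect is zero if nobody leaves before surgery. A safety set of all enrolled subjects is also reasonable here: events are collected from consent, and section 13.1 counts events that occur before any treatment.
- A reader might infer that the investigator alone decides what counts as related. Subsection 12.3.1 gives the Medical Monitor a parallel assessment. The defect is that 13.5 does not say which one applies.
- A reader might infer that unrelated ocular events are hidden. They are in the first tabulation.

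**Conclusion.** The concern holds in a limited form. Followed as written, 13.5 leaves non-ocular events judged unrelated out of every planned table, includes no summary of serious adverse events, and does not identify the causality assessor. This follows from the text and needs no assumption.

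Each omitted subject with such an event is 2.9% of 35. How often this would happen depends on an assumed event rate: roughly an even chance of at least one at 2% per subject, and about five in six at 5%.

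The absence of a stated divisor and counting unit is a secondary gap. The unit could change an ocular percentage by a factor of two. Any dilution from never-operated subjects is conditional: for a single event it is at most 2.86 − 2.50 = 0.36 percentage points with up to five such subjects, and nil with none.

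The point concerns completeness of safety reporting in a descriptive single-arm study. It does not touch the primary outcome, but the remedy is cheap enough to be worth making.

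**What to change.** Amend section 13.5 to:

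- summarise all adverse events and, separately, all serious adverse events, ocular and non-ocular, overall and by relatedness;
- state whose causality judgement is used, for example related if either the investigator or the Medical Monitor says so;
- report ocular events per eye and per subject, and non-ocular events per subject;
- show the number operated alongside the number enrolled, and list events in never-operated subjects separately.

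The safety population in section 10.1 can stay as all enrolled subjects.

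The cost is wording and one or two extra tables. Section 13.3 already collects the data, so no new assessment is needed. Reported event counts may be slightly higher than under the present plan.
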